STATEMENT OF COMPLIANCE

The trial will be conducted in accordance with International Conference on Harmonisation Good Clinical Practice (ICH GCP) and applicable United States (US) Code of Federal Regulations (CFR). The Principal Investigator will assure that no deviation from, or changes to, the protocol will take place without prior documented approval from the Institutional Review Board (IRB), except where necessary to eliminate an immediate hazard(s) to the trial subjects. All personnel involved in the conduct of this study have completed Human Subjects Protection and ICH GCP Training.

The protocol, informed consent form(s), recruitment materials, and all subject materials will be submitted to the local Institutional Review Board (IRB) for review and approval. Approval of both the protocol and the consent form must be obtained before any subject is enrolled. Any amendment to the protocol will require review and approval by the IRB before the changes are implemented to the study. All changes to the consent form will be IRB approved; a determination will be made regarding whether a new consent needs to be obtained from subjects who provided consent, using a previously approved consent form.

1 PROTOCOL SUMMARY

1.1 SYNOPSIS

Title:	Intervention mapping to adapt a mindfulness-based intervention for adults with diabetes and emotional distress
Study Description:	This study will pilot test the content of a Mindfulness-Based Diabetes Education program with adults who have type 2. The program integrates two evidence-based interventions – Mindfulness-Based Stress Reduction and Diabetes Self-Management Education. This pilot study will assess the acceptability, feasibility, and preliminary efficacy of the intervention. Participants' input will be used to adapt and improve the program to best fit the target study population.. This study will enroll up to 30 participants by the University of Alabama at Birmingham in conjunction with Cooper Green Mercy Healthcare Services Authority.
Objectives:	To pilot test an integrated Mindfulness-Based Stress Reduction/Diabetes Self-Management Education intervention in a small group of participants to assess acceptability and feasibility.
Endpoints:	Feasibility, Acceptability, Preliminary Efficacy
Study Population:	Adults with type 2 diabetes
Phase:	Single Arm Pilot Study
Description of Study Intervention:	This is a new program that combines Mindfulness-Based Stress Reduction and Diabetes Self-Management Education. If you enter and complete this study, you will be in this study for a total of 2 months. The Mindfulness-Based Diabetes Education program will be held weekly, in-person, in a group setting. Over 2 months, you will have eight weekly sessions for the program with a trained facilitator and other study participants. You will

	receive a schedule at the beginning of the program with the sessions outlined. The group sessions will occur every week. Approximately 5-10 participants will be assigned to each group.
Study Duration:	12 months
Subject Duration:	2 months

1.2 SCHEDULE OF ACTIVITIES (SOA)

Activity	Activity Schedule
Mindfulness-Based Diabetes Education program sessions	Weeks 1 to 8: meet weekly
Study assessment visits – 2	1. Enrollment assessment visit
	2. 8-week assessment visit
Focus Group – 1	1. Focus group

INTRODUCTION

1.3 STUDY RATIONALE

In this study, we will pilot an intervention (integrated mindfulness-based stress reduction and diabetes self-management education) in a small group of participants to assess acceptability, feasibility, and preliminary efficacy.

1.4 BACKGROUND

Type 2 diabetes is a chronic disease that is especially common in the Southeastern United States, affecting 14% of adults in Alabama. Low-income and racial/ethnic minority adults are disproportionately affected by type 2 diabetes. Managing type 2 diabetes requires patients to eat a healthy diet, exercise regularly, take all medications as prescribed, and monitor their blood sugar, which can be challenging for many patients.

Patients with type 2 diabetes who have elevated diabetes distress are less likely to follow the recommended treatment or to have well-controlled diabetes. Although some existing treatments help to improve distress, these treatments do not consistently improve diabetes self-management or outcomes. Information about how other psychosocial factors is associated with diabetes distress is limited. Additionally, the temporal relationship between diabetes distress and diabetes self-management behaviors has not been clearly elucidated. A better understanding of how diabetes distress is associated with other psychosocial factors and diabetes self-management behaviors will allow for the development of more effective interventions.

We applied a systematic method to develop an intervention which integrates components of mindfulness-based stress reduction and diabetes self-management education. In this study, we will pilot test this intervention in a small group of participants to assess acceptability and feasibility.

1.5 RISK/BENEFIT ASSESSMENT

1.5.1 KNOWN POTENTIAL RISKS

All participants will be treated according to the highest ethical standards. No participant will experience a reduction in medical, or any other type of needed service (e.g., social or clinical) that are currently available to him/her. Participation may involve completing a questionnaire, semi-structured interviews, or participating in the pilot study intervention (Mindfulness-Based Diabetes Education). Semi-structured interviews and focus groups will be audio-recorded, but no unique identifiers will be used in the collection of their responses. No significant risks are anticipated with this portion of the research plan than otherwise experienced in day-to-day living. The participants may experience some discomfort in talking about personal health issues, emotional distress, or diabetes management.

Breach of Confidentiality. The main potential risk of this study is breach of confidentiality. This is one of the most common risks of participation in clinical research. Accordingly, our team has designed a strategy to protect participant confidentiality. All participants will be informed of study procedures and gauged for understanding of study tasks. In addition, study personnel will follow regulatory guidelines

for obtaining informed consent. All interviews and intervention activities will be conducted in a private space. For all participants, research data will be stored using a unique participant identification code (sequence number based on entry to the study) instead of names or other personal identifiers. Consent forms with links to participant study numbers will be kept in a locked file cabinet in a locked office with the PI ([name]) or research assistant. According to UAB regulatory policy, records relating to research, including informed consent documents, shall be securely retained for one year after completion of the research. All records shall be accessible for inspection and copying by authorized representatives of the department or sponsor agency at reasonable times and in a reasonable manner. All electronic study data are kept on UAB secure encrypted password protected servers, and will only be available to research personnel for this project. All study personnel will complete HIPAA and human subjects training in accordance with UAB Institutional Review Board policy.

Emotional Distress. Participants will complete the 17-item DDS measure after informed consent is obtained, which will be scored by study personnel to determine eligibility. Additionally, measures of emotional distress will be assessed at baseline and 2-month follow-up for intervention participants. The measures assess the level of diabetes distress and depressive symptoms that a participant is experiencing, these are not diagnostic tests. Our study measures will not ask about suicidality. Participants may experience emotional distress related to participating in the intervention, due to the focus on emotional distress. Participants will be informed that they may stop participation at any time if they feel uncomfortable. Additionally, if a participant appears to be in emotional distress, study staff will inquire as to the participant's well-being and whether they wish to stop the study visit or session. Participants who disclose potentially harmful information (e.g., suicidality) will be immediately referred for an assessment by behavioral health at CGMHSA. All participants will be provided with a letter outlining services that details information on available mental health services at CGMHSA and low-cost resources available in Jefferson County.

Inconvenience. Participating in the study may inconvenience patients because of the time needed to collect data and participate in the intervention sessions.

Alternative Treatments and Procedures: All study participants, including those in the single-arm pilot intervention, will have full access to all available standard of care clinical services at CGMHSA, and are permitted to withdraw or refuse participation at any time.

1.5.2 KNOWN POTENTIAL BENEFITS

Participants may or may not benefit from the study. For participants in the pilot intervention, benefits may include improvement in emotional distress, diabetes self-management behaviors, and glycemic control. Risks to participants are related primarily to breach of confidentiality and emotional distress. As the risk to individual participants is small and potential benefits are significant, the risk/benefit ratio is favorable.

2 STUDY DESIGN

2.1 OVERALL DESIGN

This is a single-arm pilot study of Mindfulness-Based Diabetes Education (an integrated mindfulness-based stress reduction and diabetes self-management education intervention) in adults with type 2 diabetes who receive care at a safety-net healthcare system. Participants will complete baseline and 2-

month assessments, as well as a focus group after study completion. Program will be delivered over 8-weekly group educational sessions, in-person with 5-10 participants per group.

2.2 END OF STUDY DEFINITION

Date of final visit for participant follow up assessment.

3 STUDY POPULATION

3.1 INCLUSION CRITERIA

Inclusion criteria:

- age 19-64 years
- diagnosis of type 2 diabetes
- receipt of care at CGMHSA (one or more visits to primary care or diabetes clinic within the prior year)

3.2 EXCLUSION CRITERIA

Exclusion criteria:

- non-English speaking
- currently pregnant
- personal history or prior diagnosis of bipolar disorder, schizophrenia, or psychosis

3.3 SCREEN FAILURES

<Insert text>

3.4 STRATEGIES FOR RECRUITMENT AND RETENTION

Study participants will be recruited from Cooper Green Mercy Health System Authority (CGMHSA). At CGMHSA, a report of patients who have been referred to diabetes education from 2017-2020 was generated to identify potential study participants. Letters will be mailed to participants (letters included), followed by a phone call to inform them of the study (phone script included), conduct screening listed below, and if participants are interested to schedule a study visit.

Additionally, potential participants may be identified through screening in the CGMHSA diabetes clinic or primary care clinic. CGMHSA clinicians will provide contact information (names, phone numbers) for potential participants seen in diabetes or primary care clinics who agree to be contacted about the study. Similar to the process described above, study personnel will call potential participants by phone to inform them of the study (phone scripts included), conduct screening listed below, and if participants are interested to schedule a study visit.

Study PI will inform CGMHSA primary care providers of the study and eligibility criteria (providing a study recruitment flyer); primary care providers will be asked to have any interested potential participants to contact study personnel at the number listed on the flyer.

If participants contact study personnel after seeing a study flyer or after learning of the study from their primary care provider, study staff will speak to potential participants by phone (upon call from potential participant or by returning a phone call to the potential participant), provide additional information about the study, conduct screening listed below, and if participants are interested to schedule a study visit. During the recruitment phone call, study staff will explain the research project.

4 STUDY INTERVENTION

4.1 STUDY INTERVENTION(S) ADMINISTRATION

4.1.1 STUDY INTERVENTION DESCRIPTION

We will recruit up to 30 participants to complete the pilot intervention, in groups of 5-10 participants. The program will be delivered in 8 weekly sessions of 1.5 to 2 hours duration each, for a total duration of 2 months. The pilot intervention will be delivered by study PI, [name], who is an Internal Medicine-Pediatrics trained physician with training in delivery of mindfulness-based interventions. We have included the intervention manual with this amendment/revision. Program sessions will be recorded solely for the purposes of assessing fidelity to intervention content. Any identifying information will be removed from transcripts. The following table provides overview of session content with full details in the manual.

Table: Mindfulness-Based Diabetes Education Sessions and Content	
Session	Session Content
1	
 Introduction to mindfulness; body scan meditation Introduction to behavior change and diabetes
2	
 Role of perception, stress responses and reactivity; breath awareness meditation Healthy eating module with mindful eating of healthy snack w/reflection on thoughts, emotions, physical sensations Pleasant events calendar w/focus on events related to diabetes self-management
3	
 Exploration of mind-body connections Physical activity (PA) module, mindful walking with attention to thoughts, emotions, physical sensations related to PA Unpleasant events calendar w/focus on events related to diabetes self-management
4	
 Mindfulness as means to reduce negative effects of stress, mindful yoga Healthy eating module SMART goal setting focused on diabetes self-management
5	
 Exploration of coping mechanisms, capacity for mindful responding; breath awareness meditation Self-monitoring blood glucose module SMART goal setting focused on diabetes self-management
6	
 Integration of mindfulness into daily life; breath awareness meditation Medication taking module SMART goal setting focused on diabetes self-management

7	
 • Mindfulness and interpersonal communication; mindful walking • Problem solving module • SMART goal setting focused on diabetes self-management
8	
 • Focus on continued formal and informal practice; guided reflection • Framework for mindfulness and influence on diabetes

4.1.2 DOSING AND ADMINISTRATION

The program will be delivered in a group setting for 8 weekly sessions of 1.5 to 2 hours duration each, for a total duration of 2 months.

4.2 STUDY INTERVENTION COMPLIANCE

<Insert text>

4.3 CONCOMITANT THERAPY

No changes to participants' medication regimen will be made during the study. Participants will be instructed to continue taking medications prescribed by their healthcare provider. Additionally, participants who are engaged in mental health treatment, including psychotherapy, will be able to continue this treatment unchanged during their participation in this study.

5 STUDY INTERVENTION DISCONTINUATION AND SUBJECT DISCONTINUATION/WITHDRAWAL

5.1 DISCONTINUATION OF STUDY INTERVENTION

This study will be stopped prior to its completion if: (1) the intervention is associated with adverse effects that call into question the safety of the intervention; (2) difficulty in study recruitment or retention will significantly impact the ability to evaluate the study endpoints; (3) any new information becomes available during the trial that necessitates stopping the trial; or (4) other situations occur that might warrant stopping the trial.

5.2 SUBJECT DISCONTINUATION/WITHDRAWAL FROM THE STUDY

Subjects are free to withdraw from participation in the study at any time upon request.

An investigator may discontinue or withdraw a subject from the study for the following reasons:

- Significant study intervention non-compliance
- If any clinical adverse event (AE), laboratory abnormality, or other medical condition or situation occurs such that continued participation in the study would not be in the best interest of the subject

Subjects who sign the informed consent form and are randomized but do not receive the study intervention may be replaced. Subjects who sign the informed consent form, and are randomized and receive the study intervention, and subsequently withdraw, or are withdrawn or discontinued from the study, will not be replaced.

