5.3 LOST TO FOLLOW-UP

A subject will be considered lost to follow-up if he or she fails to return for 2 scheduled visits and is unable to be contacted by the study site staff.

The following actions must be taken if a subject fails to be available for a required study visit:

- The site will attempt to contact the subject and reschedule the missed visit and counsel the subject on the importance of maintaining the assigned visit schedule and ascertain if the subject wishes to and/or should continue in the study.
- Before a subject is deemed lost to follow-up, the investigator or designee will make every effort to regain contact with the subject (where possible, 3 telephone calls and, if necessary, a certified letter to the subject's last known mailing address or local equivalent methods). These contact attempts should be documented in the subject's medical record or study file.
- Should the subject continue to be unreachable, he or she will be considered to have withdrawn from the study with a primary reason of lost to follow-up.

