6 STUDY ASSESSMENTS AND PROCEDURES

6.1 STUDY ASSESSMENTS

Participants will complete assessment at baseline and 2 months. Assessments will include interviewer-administered measures. Participants will also participate in a focus group for acceptability following completion of the intervention. Process measures for feasibility will be tracked throughout the study.

Acceptability, focus groups:

- assessment of intervention content
- perceived positive or negative effects
- appropriateness of intervention duration and frequency
- barriers to engagement, suggestions to improve the intervention
- overall satisfaction

Feasibility of the intervention using process measures:

- percentage of screened participants who are eligible
- percentage of eligible participants who enroll
- distribution of participants by demographics (age, race, ethnicity, gender)
- number of sessions attended
- participant adherence to study tasks
- overall study retention

Preliminary efficacy: baseline and 2-month follow-up:

- diabetes distress (Diabetes Distress Scale)
- diabetes self-management behaviors (Adherence to Refills and Medications scale, Summary of Diabetes Self-Care Activities)

- glycemic control (A1C test results from electronic medical records)

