6.2.4 TIME PERIOD AND FREQUENCY FOR EVENT ASSESSMENT AND FOLLOW-UP

The occurrence of an adverse event (AE) or serious adverse event (SAE) may come to the attention of study personnel during study visits and interviews of a study subject presenting for medical care, or upon review by a study monitor.

All AEs including local and systemic reactions not meeting the criteria for SAEs will be captured on the appropriate case report form (CRF). Information to be collected includes event description, time of onset, clinician's assessment of severity, relationship to study product (assessed only by those with the training and authority to make a diagnosis), and time of resolution/stabilization of the event. All AEs occurring while on study must be documented appropriately regardless of relationship. All AEs will be followed to adequate resolution.

Any medical condition that is present at the time that the subject is screened will be considered as baseline and not reported as an AE. However, if the study subject's condition deteriorates at any time during the study, it will be recorded as an AE.

Changes in the severity of an AE will be documented to allow an assessment of the duration of the event at each level of severity to be performed. AEs characterized as intermittent require documentation of onset and duration of each episode.

The Study Coordinator will record all reportable events with start dates occurring any time after informed consent is obtained until 7 (for non-serious AEs) or 30 days (for SAEs) after the last day of study participation. At each study visit, the Study Coordinator will inquire about the occurrence of AE/SAEs since the last visit. Events will be followed for outcome information until resolution or stabilization.

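### Section 5.2 allows withdrawal from the whole study for undefined intervention non-compliance and does not separate stopping the sessions from leaving follow-up, so poorly engaged participants may be missing from the acceptability data

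*Combined protocol and SAP*

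**What the plan says.** Section 5.2 opens its list with "An investigator may discontinue or withdraw a subject from the study for the following reasons". The first reason is "Significant study intervention non-compliance"; the second is a safety ground. The object of the withdrawal is the study, not the weekly sessions. People withdrawn after receiving the intervention are not replaced.

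Section 4.2, where compliance would be defined, is an unfilled template placeholder. Section 6.1 lists session attendance and adherence to study tasks as two separate process measures.

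The neighbouring sections do not describe a person who stops the sessions but stays in for assessment. Section 5.1 is headed as discontinuation of the intervention, but its content begins "This study will be stopped prior to its completion if" and covers stopping the whole study. Section 5.3 deals with missed visits; the contact there is to "ascertain if the subject wishes to and/or should continue in the study".

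The default for everyone else is inclusive. Section 2.1 has participants complete baseline and 2-"month assessments, as well as a focus group after study completion". Section 6.1 says "Participants will also participate in a focus group for acceptability following completion of the intervention", and its list of focus-group topics includes "barriers to engagement, suggestions to improve the intervention". Neither section sets an attendance condition.

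For safety data the plan does look past a person's exit: section 6.2.4 records events "until 7 (for non-serious AEs) or 30 days (for SAEs) after the last day of study participation", though it does not mention withdrawal by name. There is no similar sentence for the questionnaires or the focus group.

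**The concern.** The objective in section 1.1 is acceptability and feasibility, and participants' input is to be used to adapt the program. Section 7.3.1 says efficacy will not be estimated. The focus group is therefore a main source of evidence, and what keeps people from engaging is one of the things it is meant to find out.

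A rule that takes people out of the study because they did not comply with the intervention selects on engagement. Where it is used, it removes people likely to have first-hand experience of those barriers. Their 2-month distress and self-management questionnaires go with them. The adaptation would then draw more heavily on people for whom the format already worked.

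**Working it through.** **1. Is there a route for stopping sessions and staying in?** Reading the sections together:

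- 5.1: whole-study stopping only.
- 5.2: exit from the study, with non-compliance as one ground.
- 5.3: missed visits and unreachable participants; nothing on those whom the investigator withdraws.
- 1.2: an enrollment visit, an 8-week visit and a focus group; no early-termination visit.
- 6.1: assessments and focus group for participants; no provision for those withdrawn.
- 6.2.4: adverse events only.

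No such route appears in the supplied text.

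**2. How many could be lost?** The plan gives no rate, so all of these are assumptions. Take the full 30 (the plan says up to 30) and let k = 3, 6 or 9 be withdrawn on this ground and not assessed. Coverage of the 2-month questionnaires is at most (30 − k)/30. For the focus group, if each withdrawn person were invited and accepted independently with probability a, the chance that at least one is heard is 1 − (1 − a)^k.

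| k withdrawn | With questionnaires, at most | Heard, no invitation | At least one heard, a = 0.2 | At least one heard, a = 0.5 |
|---|---|---|---|---|
| 3 | 27/30 = 90% | 0 | 1 − 0.8^3 = 49% | 1 − 0.5^3 = 88% |
| 6 | 24/30 = 80% | 0 | 1 − 0.8^6 = 74% | 1 − 0.5^6 = 98% |
| 9 | 21/30 = 70% | 0 | 1 − 0.8^9 = 87% | 1 − 0.5^9 = 99.8% |

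The zero column follows from assuming that silence about an invitation means none is made. It counts only the withdrawn, not every poorly engaged participant.

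**3. Would mean change be distorted?** Suppose the withdrawn differ from the rest by 0.5 SD in mean distress change, in either direction (an assumption). The mean among those left then differs from the mean of all starters by (k/30) × 0.5 SD = 0.05, 0.10 or 0.15 SD. The standard error, 1/√n at n = 27, 24 and 21, is 0.19, 0.20 and 0.22 SD. The ratios are 0.26, 0.49 and 0.69. Each shift is below one standard error, and its direction is unknown.

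**4. Does power matter here?** The plan's only related figure is in section 7.2: SD of HbA1c change 1.8%, n = 30, two-sided paired t-test at 0.05, 80% power for a change of 1.0%. With the noncentral t (29 degrees of freedom, noncentrality (1.0/1.8) × √30 = 3.04), power is 83.7%. The smallest n reaching 80% is 28, so the plan's figure holds. If paired A1C were lost for k people, power would be 79.4%, 74.1% or 67.8%. But section 7.3.1 rules out formal testing, and A1C comes from medical records, so it need not be lost. This is not a reason for the change.

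**The case against.** Several objections are fair.

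- **Discretion and default.** The rule is permissive and may never be used. Section 5.2 also speaks of randomized subjects in a single-arm study, which suggests template text. Anyone not withdrawn remains covered by 2.1 and 6.1, and the phrase in 6.1 about completing the intervention can be read as timing, not as a completers-only rule. This stands: the loss is possible, not certain, and poorly engaged people who are not withdrawn can still speak. But the default covers only people still in the study, and 5.2 is the way out of it.
- **Non-compliance is not the same as low attendance.** A reader might infer that everyone lost this way would be a low attender. The documents do not support that: 4.2 is blank, and 6.1 lists attendance and task adherence separately. Some low attenders among the withdrawn is probable, but it is an assumption.
- **Invented rates.** The counts and acceptance rates are illustrative, and independence of acceptance is assumed. They show how the mechanism works; they do not predict its size.
- **Other data survive.** Attendance and medical-record A1C may still be available. Neither explains why someone disengaged, and the questionnaires would still be missing.
- **Unseen material.** The consent form and the intervention manual were not part of the text reviewed and could address this. The finding is therefore limited to the supplied text.

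**Conclusion.** The point holds as a modest design improvement. As written, 5.2 lets an undefined degree of intervention non-compliance end study participation, and nothing in the supplied text keeps such a person in the 8-week assessment or focus group. Where the rule is used, the acceptability evidence loses poorly engaged participants. The frequency is unknown; for 3 to 9 of 30, questionnaire coverage would be at most 90% to 70%.

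Two stronger readings are tempting. One is that low attenders as a group will be excluded: that does not follow from a discretionary rule with an undefined trigger. The other is that the descriptive mean changes will be materially biased or the study underpowered: the illustrative shifts are under one standard error, their sign is unknown, and the plan disclaims efficacy estimation. The case rests on whose experience informs the adaptation.

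**What to change.** In 5.2, make intervention non-compliance a ground for ending participation in the sessions only, not for withdrawal from the study. State in 5.2, and in one sentence in 6.1, that participants who stop the sessions and have not withdrawn consent are still invited to the 8-week assessment and the focus group. Leave the safety-based ground unchanged. The change concerns data collection only.

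The cost is a sentence or two in each section, IRB review of the amendment and a few extra invitations. Some of those invited will decline, so the gap narrows but does not close.
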